1.4 Study Design

The study is an open label, single arm study with flexible dose regimen focused on assessing long-term safety and tolerability of ZS in Japanese subjects with hyperkalemia.

Correction Phase: If the subject is normokalemic (i-STAT potassium between 3.5 and 5.0 mmol/L, inclusive) on the morning of Correction Phase Study Day 2 after 3 doses of ZS 10 g, they will enter the Maintenance Phase. If the subject is not normokalemic, they will receive an additional 24 hours of ZS 10 g TID treatment (6 total doses). If the subject's i-STAT potassium value is between 3.5 and 5.0 mmol/L, inclusive, on the morning of Correction Phase Study Day 3, the subject will enter the Maintenance Phase. If the subject is not normokalemic, they will receive an additional 24 hours of ZS 10 g TID treatment (9 total

doses). If the subject's i-STAT potassium value is between 3.5 and 5.0 mmol/L, inclusive, on the morning of Correction Phase Study Day 4, the subject will enter the Maintenance Phase. If the i-STAT potassium value is still < 3.5 mmol/L or ≥ 5.1 mmol/L on the morning of Correction Phase Study Day 4, after 72 hours of TID treatment, the subject will be withdrawn from the study and referred to their normal health care provider for standard of care treatment. Subjects withdrawn from the Correction Phase of the study will return to the clinic $7 (\pm 1)$ days after their last dose of ZS for an End of Study (EOS) visit.

[figure not shown]
Maintenance Phase: Patients will initially be dosed with ZS at a starting dose of 5g QD. Potassium (i-STAT and central laboratory) will be measured as indicated in the study schedule (Table 2). During the Maintenance Phase, the ZS dose may be increased up to 15 g QD or decreased down to 5g QOD (or 2.5 g QD) based on i-STAT potassium measurements as outlined in Section 7.2.

Throughout all phases of the study, most potassium values will be measured at fasting before taking ZS. Nothing should be taken by mouth except water, coffee or tea, with or without milk and/or sugar, and essential medications, for a minimum of 8 hours prior to the blood collection. Potassium level should be determined by both i-STAT and the Central Laboratory on all occasions. Treatment decisions (eg, dose titration, stopping rules) will be made based on i-STAT potassium values, as these provide clinical sites with a real-time measurement, according to dose modification rules as described in Section 7.2. Statistical analyses on the study data will in principle be based on S-K values as measured by the Central Laboratory.

Safety and tolerability will be assessed on an ongoing basis. Standard study assessments including blood potassium, clinical chemistry (including calcium, magnesium, sodium, phosphate, creatinine, bicarbonate, and blood urea nitrogen [BUN]), aldosterone, renin and hematology parameters, urinalysis, vital signs, physical examinations, and electrocardiograms (ECGs) will be assessed during the study at the time points specified in Table 1 and Table 2. All women of childbearing potential will have a urine pregnancy test prior to enrollment and at their End of Study (EOS) visit.

Stopping rules will be implemented to ensure subjects discontinue the study treatment and receive alternative therapy in case of significant hyperkalemia, hypokalemia, arrhythmias, or development of congestive heart failure or end stage renal failure.

Figure 3 Study flow chart

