Correction Phase: If the subject is normokalemic (i-STAT [A portable blood analyser] potassium between 3.5 and 5.0 mmol/L, inclusive) on the morning of Correction Phase Study Day 2 after 3 doses of ZS 10 g, they will enter the Maintenance Phase. If the subject is not normokalemic, they will receive an additional 24 hours of ZS 10 g TID treatment (6 total doses). If the subject's i-STAT potassium value is between 3.5 and 5.0 mmol/L, inclusive, on the morning of Correction Phase Study Day 3, the subject will enter the Maintenance Phase. If the subject is not normokalemic, they will receive an additional 24 hours of ZS 10 g TID treatment (9 total doses). If the subject's i-STAT potassium value is between 3.5 and 5.0 mmol/L, inclusive, on the morning of Correction Phase Study Day 4, the subject will enter the Maintenance Phase. If the i-STAT potassium value is still < 3.5 mmol/L or ≥ 5.1 mmol/L on the morning of Correction Phase Study Day 4, after 72 hours of TID treatment, the subject will be withdrawn from the study and referred to their normal health care provider for standard of care treatment. Subjects withdrawn from the Correction Phase of the study will return to the clinic 7 (± 1) days after their last dose of ZS for an End of Study (EOS) visit.

Maintenance Phase: Patients will initially be dosed with ZS at a starting dose of 5g QD. Potassium (i-STAT and central laboratory) will be measured as indicated in the study schedule (Table 2). During the Maintenance Phase, the ZS dose may be increased up to 15 g QD or decreased down to 5g QOD (or 2.5 g QD) based on i-STAT potassium measurements as outlined in Section 7.2.

Throughout all phases of the study, most potassium values will be measured at fasting before taking ZS. Nothing should be taken by mouth except water, coffee or tea, with or without milk and/or sugar, and essential medications, for a minimum of 8 hours prior to the blood collection. Potassium level should be determined by both i-STAT and the Central Laboratory on all occasions. Treatment decisions (eg, dose titration, stopping rules) will be made based on i-STAT potassium values, as these provide clinical sites with a real-time measurement, according to dose modification rules as described in Section 7.2. Statistical analyses on the study data will in principle be based on S-K values as measured by the Central Laboratory.

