4. STUDY PLAN AND TIMING OF PROCEDURES

Table 1 Study Plan for the Correction Phase

Study Visit	Visit 1	Visit 2 ⁷	Visit 3 ⁵	Visit 4 ⁵	Visit 5 ⁵	EOS ⁶
Correction Phase Day	Screening	Day 1 ⁷	Day 2 ⁵	Day 3 ⁵	Day 4 ⁵	Day 10 ⁶
Written informed consent	X					
Eligibility criteria		X				
Demographics	X					
Medical History		X				
SF-36 v2 questionnaire		X				
Physical exam including weight		X ⁸				X ⁸
Access IVRS/IWRS	X	X	X ⁹	X ⁹	X ⁹	
Study drug (IP) dispensation		X	X ⁹	X ⁹		
Study drug (IP) administration		X	X ⁹	X ⁹		
ECG		X	X ⁹	X ⁹	X ⁹	X
Vital signs		X		X ⁹	X ⁹	X
Concomitant medications		X	X	X	X	X
Adverse events		X ¹⁰	X	X	X	X
Potassium ¹		X ²	X ^{3,11}	X ¹¹	X ¹²	X ¹²
Serum Chemistry ¹		X			X ⁹	X
Hematology ¹		X			X ⁹	X
Aldosterone and renin ¹		X				
Urinalysis ¹		X			X ⁹	X
Urine HCG		X ⁴				X ⁴
IP Reconciliation						X

- All blood potassium samples are analyzed by i-STAT and by the Central Laboratories on all occasions. Serum clinical chemistry, including S-K, hematology and urinalysis will be measured fasting and before administration of ZS. For diabetic patients all blood potassium samples should be collected prior to insulin administration whenever possible.
- Blood potassium will be measured twice 60 (±15) minutes apart within 1 day of first dose administration on Correction Phase Day 1(Visit 2) and at 4 hours (±15 min) after administration of the first dose of ZS. Potassium will be measured again at 90 minutes (±15 minutes) after taking the second dose for patients with i-STAT potassium ≥6.1 mmol/L or <4.0 mmol/L 4 hours after the first dose. The Central Laboratory serum chemistry, hematology, aldosterone and renin samples will be collected at the same time as the 60 minutes i-STAT screening potassium sample, but will be analysed only in confirmed hyperkalemic subjects.

3. Potassium will be measured predose (0 hour) and 1 hour (± 15 min) after the first dose on Correction Phase Day 2 (Visit 3).
4. U-HCG will be performed exclusively for women of childbearing potential. Samples will be analysed locally, and the data will not need to be collected in the database. Pregnant women are excluded from the study.
5. Visit 3, 4 and 5 (Day 2, 3 and 4 for the Correction Phase) are the same as visit 6 Day 1 in the Maintenance Phase for patients achieving normokalemia in the morning the day of the visit. Patients not achieving normokalemia at Visit 4 will be dosed with ZS 10g TID for an additional 24h and then return to the site for Visit 5.

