6. EOS in Correction Phase only for patients NOT entering the Maintenance Phase, and occurs 7 ± 1 day after the last administration of IP.
7. Baseline parameters should be measured/collected no earlier than 1 day prior to administration of the 1st dose of study drug on Day 1 (Visit 2). Visits 1 and 2 may be combined into a single visit on the same day.
8. A complete physical examination should be performed within 1 day of administration of the first dose of study drug on Correction Phase Day 1, and targeted physical examination will be conducted on EOS.
9. If subject does not qualify for the Maintenance Phase on/before Correction Phase Day 4.
10. AEs will be collected after the patient has signed informed consent, so during the Day 1 (Visit 2), investigator need to check if any AE happened since from inform consent.
11. Blood potassium will be measured upon return to the clinic to determine if the subject is eligible to enter the Maintenance Phase or if the subject should receive an additional 24 hours of dosing.
12. Central laboratory potassium sample collected as part of the serum chemistry panel.

Table 2 Study Plan for the Maintenance Phase

Study Visit (Visit)	6	7	8	9	10	11	12	13	14	15	16	17	18	19	20	21	22	23	EOS	
Maintenance Phase Day⁵ (Day)	1	2	5	12	19	26	54	82	110	138	166	194	222	250	278	306	334	362	One week after last IP⁶	
Targeted physical exam including weight	X			X		X	X	X	X	X	X	X	X	X	X	X	X	X	X	X
SF-36 v2 questionnaire																				X
Access IVRS/TWRS ⁷	X			X		X	X	X	X	X	X	X	X	X	X	X	X	X	X	X
Study drug (IP) dispensation	X			X		X	X	X	X	X	X	X	X	X	X	X	X	X	X	X
Study drug (IP) administration	X			X		X	X	X	X	X	X	X	X	X	X	X	X	X	X	X
ECG	X			X		X	X	X			X			X			X			X
Vital signs	X			X		X	X	X	X	X	X	X	X	X	X	X	X	X	X	X
Concomitant medications	X			X		X	X	X	X	X	X	X	X	X	X	X	X	X	X	X
Adverse events	X			X		X	X	X	X	X	X	X	X	X	X	X	X	X	X	X
Potassium ^{1,2}	X ^{2,3,8}	X ^{2,8}	X ^{2,8}	X ^{2,8}	X ^{2,8}	X ^{2,8}	X ^{2,8}	X ^{2,8}	X ^{2,8}	X ^{2,8}	X ^{2,8}	X ^{2,8}	X ^{2,8}	X ^{2,8}	X ^{2,8}	X ^{2,8}	X ^{2,8}	X ^{2,8}	X ^{2,8}	X ^{2,8}
Serum chemistry ¹	X			X		X	X	X			X			X			X			X
Hematology ¹				X		X	X	X	X	X	X	X	X	X	X	X	X	X	X	X

Table 2 Study Plan for the Maintenance Phase

Study Visit (Visit)	6	7	8	9	10	11	12	13	14	15	16	17	18	19	20	21	22	23	EOS
Maintenance Phase Day ⁵ (Day)	1	2	5	12	19	26	54	82	110	138	166	194	222	250	278	306	334	362	One week after last IP ⁶
Aldosterone and renin										X									X
Urinalysis ¹					X			X		X				X			X		X

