4.2.2 Correction Phase Day 2 (Visit 3)

Subjects will arrive at the clinic in the morning after fasting for at least 8 hours prior to potassium sample collection.

- The clinic staff will solicit any adverse events, note any changes in concomitant medications, note if the subject has visited a doctor or emergency room since the last visit, examine the investigational product dosing boxes and sachets and make note of the time the doses were taken and any unused investigational products on the eCRF and source documents.
- Potassium values will be evaluated by i-STAT and the Central Laboratory.
- If the i-STAT potassium value is between 3.0 and 3.4 mmol/L inclusive, the subject should not take a study IP doses that day and return the next day to assess potassium.
 - 1 hour (± 15 min) after first serum potassium measurement a potassium sample (i-STAT and Central Laboratory) will be collected.
- If the i-STAT potassium value is between 3.5 and 5.0 mmol/L, inclusive, the subject will enter the Maintenance Phase and complete the procedures detailed in Section 4.2.5.
- If the i-STAT potassium value is ≥ 5.1 mmol/L, the subject will receive an additional 24 hours of ZS 10 g TID and the following procedures will be performed:
 - The site will access the IVRS/IWRS and provide the 7-digit subject identification number. The system will assign the subject an investigational product kit.
 - An ECG will be performed (Section 5.2.3).
 - The morning dose of ZS will be administered in the clinic as a suspension in water.

- 1 hour (\pm 15 min) after dose administration a potassium sample (i-STAT and Central Laboratory) will be collected.
 - Patients with i-STAT potassium levels ≤ 6.5 and ≥ 3.5 mmol/L at the 1 hour (\pm 15 minutes) post Dose 1 blood draw will be sent home with 2 doses of study drug and instructions on how to take ZS. They will be requested to fill out a dosing schedule card indicating when they took the IP. The patient will return to the clinic the following morning of the Correction Phase Day 3 (Visit 4).
 - If the potassium level is > 6.5 mmol/L as determined by the i-STAT at the 1 hour (\pm 15 minutes) post Dose 1 blood draw, the patient will be discontinued from the study. Patient will return to the clinic 7 (\pm 1) days later for an EOS visit.
- See section 7.2 regarding how to handle patients with potassium < 3.5 mmol/L.

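### The synopsis, Section 1.4 and Table 1 footnote 5 order more ZS 10 g TID for anyone not normokalaemic, which literally includes potassium below 3.5 mmol/L; Sections 4.2.2, 4.2.3 and 7.2 say hold or stop

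*Protocol*

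**What the plan says.** **Summary text.** The synopsis (Study design) and Section 1.4 carry the same Correction Phase paragraph. A subject with a morning i-STAT potassium of 3.5 to 5.0 mmol/L moves to the Maintenance Phase. On Day 2, otherwise: "If the subject is not normokalemic, they will receive an additional 24 hours of ZS 10 g TID treatment (6 total doses". On Day 3, otherwise: "If the subject is not normokalemic, they will receive an additional 24 hours of ZS 10 g TID treatment (9 total doses". On Day 4 the subject is withdrawn if the value is "still < 3.5 mmol/L or ≥ 5.1 mmol/L on the morning of Correction Phase Study Day 4, after 72 hours of TID treatment".

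**Schedule.** Table 1 footnote 5 (Section 4) states: "Patients not achieving normokalemia at Visit 4 will be dosed with ZS 10g TID for an additional 24h and then return to the site".

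**Operational text.** Section 4.2.2 (Day 2) says: "If the i-STAT potassium value is ≥ 5.1 mmol/L, the subject will receive an additional 24 hours of ZS 10 g TID". Section 4.2.3 has the same condition for Day 3. In both sections a value of 3.0 to 3.4 mmol/L means no study drug that day and a return visit the next day, and both send values below 3.5 to Section 7.2. For the Correction Phase, Section 7.2 withholds the rest of the day's doses at a confirmed 3.0 to 3.4 and discontinues therapy at a confirmed value below 3.0. The synopsis repeats these two rules under Investigational product, dosage and mode of administration.

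**Deferral.** The synopsis and Section 1.4 both say that treatment decisions are made on i-STAT values "according to dose modification rules as described in Section 7.2".

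**The concern.** Normokalaemia is defined with both a lower and an upper limit, so its negation covers hypokalaemia as well as hyperkalaemia. The Day 2 and Day 3 sentences and footnote 5 attach one instruction, another 24 hours of 10 g TID, to that whole negation. For a subject below 3.5 mmol/L the instruction is the opposite of the one in the visit sections and Section 7.2.

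The subject's safety that day is at stake, because the drug lowers potassium and the literal instruction gives more of it to someone whose potassium is already low. The study's primary objective is safety, and these are directive dosing sentences in the design summary and the visit schedule. No estimate, test or sample-size figure depends on the wording.

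**Working it through.** No formula applies. The check compares the two sets of rules on the morning i-STAT value of Day 2 or Day 3.

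| Morning i-STAT potassium (mmol/L) | Synopsis and Section 1.4 (Days 2 and 3); Table 1 footnote 5 (Visit 4 only) | Sections 4.2.2, 4.2.3 and 7.2; synopsis dosage section | Agree? |
|---|---|---|---|
| below 3.0 | 10 g TID for another 24 h | discontinue (confirmed) | no |
| 3.0 to 3.4 | 10 g TID for another 24 h | no more doses that day, return next day | no |
| 3.5 to 5.0 | enter Maintenance Phase | enter Maintenance Phase | yes |
| 5.1 and above | 10 g TID for another 24 h | 10 g TID for another 24 h | yes |

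1. **Value by value.** Both rules were applied to every value from 2.6 to 6.7 mmol/L in steps of 0.1, which is 42 values. They differ at 9: four at 2.6 to 2.9 (dose against discontinue) and five at 3.0 to 3.4 (dose against hold). They agree at the other 42 − 9 = 33. This concerns the morning value only. The later Day 2 stop for a value above 6.5 one hour after the dose appears only in Section 4.2.2 and is a separate matter.

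2. **After the correction.** If the summary sentences redose only at 5.1 or above, hold at 3.0 to 3.4 and discontinue below 3.0, the two rules agree at all 42 values.

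3. **Dose totals.** The fixed totals of 6 and 9 presuppose that every day was dosed in full: 3 + 3 = 6 by the Day 3 morning and 3 + 3 + 3 = 9 by the Day 4 morning. Under the operational rule, a subject who took all three Day 1 doses, was held on Day 2 and was redosed on Day 3 has 3 + 0 + 3 = 6 by the Day 4 morning. That is 48 hours of TID dosing. A subject redosed on Day 2 whose one-hour sample is then confirmed at 3.0 to 3.4 stops for the day under Section 7.2 and has 3 + 1 = 4 by the Day 3 morning. The stated totals, and the 72 hours in the Day 4 sentence, are therefore maxima.

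**The case against.** The strongest objection is that the protocol already resolves the conflict. Staff work from the visit sections, which redose only at 5.1 or above. Section 7.2 gives worked examples for Days 2 and 3. The loose paragraph itself sits in sections that defer to Section 7.2 and mention stopping rules for hypokalaemia, and the synopsis prints the hold and stop rules in its dosage section. All of this stands, and it makes actual misdosing unlikely. It does not make the sentences correct: a general deferral elsewhere does not amend an instruction to do the opposite, and footnote 5 carries no deferral of its own.

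Several stronger readings are tempting, but the documents do not support them.

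- **A definite excess dose.** A reader might convert the fixed totals into extra grams for held subjects. The synopsis elsewhere describes dosing for up to 72 hours depending on potassium. The synopsis and Section 7.2 also give 3, 6 or 9 doses as possible totals. Nothing says how many subjects would fall below 3.5.
- **Table 1 footnotes 9 and 11 as dosing orders.** Footnote 9 ("If subject does not qualify for the Maintenance Phase on/before Correction Phase Day 4") also marks ECG, vital signs and laboratory rows, so it is a schedule flag. Footnote 11 ("to determine if the subject is eligible to enter the Maintenance Phase or if the subject should receive an additional 24 hours of dosing") says why potassium is measured. Neither mentions a hold, but that is incompleteness in a schedule table.
- **The Day 4 sentence as proof that low values were meant to be redosed.** A value still below 3.5 on Day 4 fits equally well a subject held on Day 3 and reassessed, as Section 7.2 describes. The sentence shows only that the paragraph has low values in view, so 'not normokalaemic' cannot safely be read as hyperkalaemic alone.
- **A different hold trigger in the visit sections.** The 3.0 to 3.4 bullets do not repeat the 10-minute confirmation, but both sections send values below 3.5 to Section 7.2, which contains it.
- **Figure 4.** It is not shown, so nothing can be drawn from it either way.

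**Conclusion.** The contradiction is real and confined to potassium below 3.5 mmol/L. It appears in five places: the Day 2 and Day 3 sentences of the synopsis, the same two sentences of Section 1.4, and Table 1 footnote 5 for Visit 4. The intended rule is not in doubt: redose at 5.1 or above, hold at 3.0 to 3.4, discontinue below 3.0. This is a minor wording error whose literal reading runs in the unsafe direction. It is not a design flaw, and it leaves the sample size and the descriptive analyses unchanged.

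The conclusion assumes that 'not normokalemic' is the complement of the 3.5 to 5.0 range defined in the same paragraph, and that i-STAT values are read to one decimal, so that nothing falls between 5.0 and 5.1. The document gives no basis for estimating how often a site would follow the summary wording over the visit sections.

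**What to change.** 1. In the Day 2 and Day 3 sentences of the synopsis and Section 1.4 (four sentences), replace the 'not normokalemic' condition with *i-STAT potassium ≥ 5.1 mmol/L*. Write *up to* before the 6 and 9 total doses, and add *for < 3.5 mmol/L, withhold or discontinue per Section 7.2*.
2. In Table 1 footnote 5, make the same change of condition for Visit 4 and add the same pointer to Section 7.2.
3. In the Day 4 sentence of the synopsis and of Section 1.4 (two sentences), write *up to* before the 72 hours of TID treatment.

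That is 4 + 1 + 2 = 7 edits to protocol wording. They change no visit, sample, data item, sample size or analysis, and can go into the next amendment.

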2. STUDY OBJECTIVES

2.1 Primary objective

Primary Objective:	Outcome Measure:
Maintenance Phase To assess open-label, long-term (12 months) safety and tolerability for ZS in Japanese subjects with hyperkalemia (serum potassium ≥ 5.1 mmol/L).	Safety and tolerability as measured by adverse events reporting, vital signs, ECGs, physical examinations, and safety laboratory measurements.

2.2 Secondary objectives

Secondary Objectives:	Outcome Measures:
Maintenance Phase 
 To evaluate the proportion of ZS-treated subjects in whom normokalemia can be maintained over prolonged periods of time, using an individually titrated dose (5 g every other day [or 2.5 g once daily], 5 g once daily, 10 g once daily or 15 g once daily) To explore the time course of S-Aldosterone and S-Bicarbonate 	
 Proportion of patients who can maintain normokalemia (defined as S-K level of ≥ 3.5 and ≤ 5.0 mmol/L, inclusive) on ZS at each Maintenance Phase study visit Proportion of patients with average S-K ≤ 5.1 mmol/L Proportion of patients with average S-K ≤ 5.5 mmol/L Proportions of patients who were normokalemic (S-K ≥ 3.5 and ≤ 5.0 mmol/L), hypokalemic (< 3.5 mmol/L), or hyperkalemic (> 5.0 mmol/L) at each Maintenance Phase visit. Subject-level average S-K over certain period of time Observed values at visit and change from baseline in S-K over time Number of normokalemic days during Maintenance Phase Change in S-K level from the last on-treatment Maintenance Phase visit to the End of Study Change from baseline in S-Aldosterone over time Proportion of patients with normal S-Aldosterone Change from baseline in S-Bicarbonate Proportion of patients with normal S-Bicarbonate

Secondary Objectives:	Outcome Measures:

 To evaluate the health state in the study population using SF-36 v2. 	
 SF-36 v2 questionnaire

Correction Phase To assess efficacy, safety and tolerability of 10 g TID ZS in Japanese patients with hyperkalemia (serum potassium [S-K] \geq 5.1 mmol/L).
	
 Observed values and change from Correction Phase baseline in S-K Proportion of patients who achieved normokalemia at 24, 48 and 72 hours after start of dosing Safety and tolerability as measured by adverse events reporting, vital signs, ECGs, physical examinations, and safety laboratory measurements during Correction Phase

2.3 Exploratory objectives

Exploratory Objectives:	Outcome Measures:

Maintenance Phase Patient reported outcomes: To evaluate if patients prefer ZS QOD or OD using the patient questionnaire.
	
Patient questionnaire

Treatment period To explore change in doses and reasonings of the change of RAAS inhibitors during the treatment period.
	
 Proportion of subjects increased RAASi doses Proportion of subjects who decrease or discontinued RAASi doses Proportion of subjects who increased at least once RAASi due to each reason Proportion of subjects who decreased/discontinued at least once RAASi due to each reason Time to first reduction/discontinuation of RAASi

